APPENDIX II:
ADDITIONS and REVISIONS

To: [name]
From: [name]
Date: September 26, 1994

Pumpkin Unit Foods:

We had several complaints during the Diet Run-In on the Pumpkin Unit Muffins. They were described as bland and tasting like cardboard. Increasing the cinnamon and/or using a pumpkin pie spice mix instead of the cinnamon, may improve the acceptability of this product. I checked to see how significant an increase in the spices would be. Doubling the amount of cinnamon would be an increase of 3 grams for the batch totaling 1494 grams of product. This is a .2% increase in the total batch size, and individual muffins would be affected by 0.1 gram which would probably not require an increase in the muffin size. Each center may want to try these suggestions and make adjustments based on regional tastes.

Also - we received our potato & corn chips 

MOP Update - Chapter 5
10/24/94

Additional instructions for completing the FBI form:

Follow the standard rules for rounding when entering the number of alcoholic beverages consumed and # of unit foods eaten into the DELTA Data Management System (DMS). The initial version of the Food and Beverage Intake Record (FBI) only allows for a single digit with no decimal place entry into the Data Management System (DMS). Therefore:

These numbers should be rounded up or down to the nearest whole number when entering them into the DMS. Specifically, this means rounding numbers .4 and lower, down; and numbers .5 and higher, up to the nearest whole number. Both the exact number and the rounded number should be noted on the written form.

DELTA MEMORANDUM

TO: Study Coordinators and Dietitians/Diet Coordinators

COPIES TO: [name], [name] and [name]

FROM: [name] *LM*

DATE: February 22, 1995

SUBJECT: Allowances for Dietary Deviations (TO BE USED ONLY IF REQUESTED BY PARTICIPANTS) for the three Fridays in Feeding Period 3 that fall during Lent

In response to the request of three participants at Pennington, the following decisions have been made to address the needs of DELTA participants who do not want to eat meat on Fridays during Lent. Before I review the decisions that have been made to allow for this request, **LET ME EMPHASIZE AGAIN THAT THESE DEVIATIONS SHOULD ONLY BE ALLOWED IF THE PARTICIPANT INITIATES A REQUEST. THESE CHANGES ARE NOT TO BE OFFERED UNSOLICITED TO ALL PARTICIPANTS.**

IF A PARTICIPANT REQUESTS TO BE ALLOWED NOT TO EAT MEAT ON FRIDAYS DURING LENT, he/she may do the following:

1. The participant may remove the meat from the Friday lunch sandwich and not eat it. This will be recorded on the Participant Food and Beverage Intake Report (FBI) under #3; and will consequently get recorded onto a DELTA Diet Deviation Form and the Compliance Check Sheet for that participant.
2. At Friday dinner the participant may take the self-selected meal option but **MUST** take the DELTA Friday night meal as a packed meal to eat for the Saturday night dinner. This exchange of meals will be recorded as a Protocol Deviation in the Center's DELTA Log Book maintained in the kitchen at each site.

This plan should minimize deviations from the diets while making allowances for our participants religious convictions. **HOWEVER, APPROPRIATE AND ACCURATE DOCUMENTATION OF THE DEVIATIONS IS REQUIRED TO INSURE THE CONTINUED INTEGRITY OF OUR STUDY.**

Call [name], [name], [name], or me if you have questions or concerns about these decisions.

TABLE OF CONTENTS

CHAPTER 6: Postprandial Studies

6.0	Postprandial Studies	1
6.0.1	Guidelines for the Preparation and Administration of the Test Meal	1
6.0.2	Sampling for Fat Load Test	2
	Figure 6.0.2.1 Nutrient Values	3
	Figure 6.0.2.2 Nomogram for Calculating Surface Area	4
6.1	Preparation and Delivery of Meal Test	5
	Figure 6.1.1 Adding Unit Foods to Postprandial Menus	6

6.0 POSTPRANDIAL STUDIES

6.0.1 Guidelines for the Preparation and Administration of the Test Meal

1. Label container with subject's name and date of preparation.
2. Set container on scale. Adjust scale to "0" g. Add 190g heavy whipping cream to container (total weight 190g).
3. Add 25g Promod to the center of container so that it doesn't stick to the sides (total weight 215g). Mix with a stirrer to prevent lumping. Use a small rubber spatula to scrape the stirrer into the container.
4. Add 30g Nestle's Quik Chocolate Syrup (or Strawberry Syrup) (total weight 245g).
5. Add 90g Breyer's Vanilla ice cream (total weight 335g).
6. Add 22g safflower oil (total weight 357g).
7. Insert beater and mix until smooth.
8. Add five (5) drops (0.2g) Lactaid. Mix again (total weight 357.2g).
9. Add calculated amount of Aquasol A. Mix.

(Aquasol A may be added on the day of the test or 24 hours before the test, at the time the formula is prepared. If the Aquasol is added to the test meal in advance, the formula must be kept in an opaque container or put container in brown paper bag, or cardboard box, before refrigerating.)

10. Cover container with lid or Saran Wrap and refrigerate.
11. This formula is for a person with a body surface area of $2M^2$. If your participant has a body surface greater than $2M^2$, you will need to prepare extra formula by repeating steps 2 - 10.

Body surface area is read from a Nomogram using height and weight measurements (see figure 6.2.2).

12. The amount of formula needed for the participant is calculated from the following formula: $\frac{\text{Participant's Body Surface Area} \times 357.2}{2}$

- 12a. The amount of Aquasol A for each participant is calculated from the following formula: $\frac{\text{Participant's Body Surface Area} \times 2}{2}$

13. Save 5g to 10g aliquot (or as much as is available--note each weight on test tube) in a stoppered, labelled test tube (see section 6.2). Freeze.
14. Serve formula with a straw. Use a squish bottle or wash bottle to wash sides of container and straw (both inside and outside). Have subject drink the rinsings.

Participant may have water or caffeine-free diet soda during the day.

[name], M.S., R.D., C.D.E.
 Irving Center for Clinical Research
 1990

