6.0.2 Sampling for Fat Load Test

The fat formula steps 1-8 can be prepared in bulk the day prior to the study. On the day of the study, after Step 9, the amount of formula needed for each subject could be weighed out -- Step 12. Three 5 to 10g aliquots must be saved -- Step 13.

General Formula:

Cream-Whipping-Heavy	190 gms
Ice Cream - 10% Fat	90 gms
Syrup Choc Flavored	30 gms
Promod	25 gms
Safflower Oil	22 gms
5 drops Lactaid	0.2 gms
Aquasol (vitamin A)	2.0 gms

Formula must be made 24 hours prior to serving so that all lactose can be converted to glucose and galactose by Lactaid.

[figure not shown]
1. Heavy cream: Tuscan Ultrapasteurized Heavy Cream Grade A
 1 Tbsp (15 ml) = 50 calories
 6g fat
 3g SFA
 10mg cholesterol
 5mg Na⁺
 10% fat ice cream is Breyer's Vanilla
 Syrup is Nestle's Quik - you can also use the Strawberry flavor
2. Vitamin A (Aquasol) must be added on the day of the study. Aquasol A drops .1ml has 5000 usb is manufactured by Armaur Pharmaceutical Co. Kankakee, Illinois 60901 for ASTRA USA Inc., Westborough, MA 01581.

Promod is from Ross Laboratories, Columbus, OH.

Figure 6.0.2.1 Nutrient Values

Nutrient Values			
+ Kilocalories	1237 kc	Protein	32.714 Gm
+ Carbohydrate	47.786 Gm	+Fat	105 Gm
Fiber-Crude	0.060 Gm	+Cholesterol	300 Mg
+Saturated Fat	52.008 Gm	Oleic Fat Acid	22.811 Gm
+Linoleic FA	18.154 Gm	+Sodium	240 Mg
+Potassium	725 Mg	Magnesium	42.252 Mg
Iron	0.611 Mg	Zinc	1.630 Mg
Vitamin A	3161 IU	Vitamin D	190 IU #
Vitam. E/Total	9.899 Mg	Vitamin C	1.575 Mg
Thiamin	0.085 Mg	Riboflavin	0.455 Mg
Niacin	0.323 Mg	Vitamin B6	0.093 Mg
Folate	10.415 Ug	Vitamin B12	0.765 Ug
+Pantoth. Acid	0.931 Mg	Calcium	247 Mg
Phosphorus	402 Mg	+Tryptophan	181 Mg
+Threonine	512 Mg	+Isoleucine	623 Mg
+Leucine	994 Mg	+Lysine	814 Mg
+Methionine	227 Mg	+Cystine	130 Mg
+Phenylalanine	583 Mg	+Tyrosine	536 Mg
+Valine	764 Mg	+Histidine	281 Mg
Alcohol	0.000 Gm	Ash	1,964 Gm
+Copper	0.289 Mg #	+Manganese	0.114 Mg #
Iodine	35.120 Ug #	+Mono Fat	25.454 Gm
+Poly Fat	19.184 Gm	Caffeine	4.200 Mg
+Fluoride	57.000 Ug #	+Molybdenum	No Data #
Vitamin K	11.336 #	Selenium	0.001 Mg #
+Biotin	0.057 Ug #	+Chloride	No Data #
+Chromium	No Data #	Sugar	27.485 Gm
Fiber-Dietary	0.071 Gm	Vit. E/AT	7.542 Mg #

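### Fat-load test meal: sections 6.0.1 and 6.0.2 disagree on the day vitamin A is added, and the step order in 6.0.1 scales the vitamin A dose by body surface area twice (minor)

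*Protocol*

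**What the plan says.** **Day of addition.** A note under step 9 of section 6.0.1 states that "Aquasol A may be added on the day of the test or 24 hours before the test" and gives light-protection rules for formula dosed in advance, so early addition is a deliberate option. Note 2 of section 6.0.2 states "Vitamin A (Aquasol) must be added on the day of the study". The opening of 6.0.2 also leaves only steps 1 to 8 for the day before.

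**Amount.** In section 6.0.1:
- Step 1: "Label container with subject's name and date of preparation", so the batch belongs to one person.
- Steps 2 to 8 build the mixture to 357.2 g.
- Step 9: "Add calculated amount of Aquasol A. Mix".
- Step 11: "This formula is for a person with a body surface area of" 2 m²; for a larger person, steps 2 to 10 are repeated.
- Step 12: "The amount of formula needed for the participant is calculated from the following formula", namely BSA × 357.2 / 2.
- Step 12a: "The amount of Aquasol A for each participant is calculated from the following formula", namely BSA × 2 / 2.

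Section 6.0.2 names step 12 as the weighing-out and places it after step 9. Its General Formula lists 2.0 g of Aquasol alongside the 357.2 g of other ingredients.

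**The concern.** On the day, one section permits what the other forbids. Four centers could follow different rules and each cite the manual.

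On the amount, formulas 12 and 12a are each correct, but they are applied in the wrong order. The only calculated Aquasol amount in 6.0.1 is 12a, which is already scaled to the participant. Step 9 puts it into a batch sized for 2 m², and the participant then drinks only BSA/2 of that batch. Anyone below 2 m² gets less vitamin A than 12a intends, and the gap widens as BSA falls. A center following 6.0.2 with the General Formula gives essentially the right dose, so the dose depends on which printed text is used.

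What is at stake is the retinyl ester measurement after the fat load, which Chapter 8 (Table 4 and section V.D) schedules with its own assay. Form PP2 records the weight of fat load offered and left over, but neither the amount nor the time of Aquasol, so a difference in route would not show in the form data.

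**Working it through.** **The protocol's own figure.** Cream 190 + Promod 25 + syrup 30 + ice cream 90 + safflower oil 22 + Lactaid 0.2 = 357.2 g. This matches step 8.

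**Assumptions.** BSA from 1.5 to 2.0 m² (the protocol gives no range), and 12a in grams as in the General Formula (12a prints no unit).

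**Route A: 6.0.1 in printed order, one-subject batch, BSA ≤ 2.**
- Target (12a) = BSA × 2 / 2 = BSA grams.
- The batch after step 9 weighs 357.2 + BSA grams and holds BSA grams of Aquasol.
- The portion (step 12) is BSA × 178.6 g.
- Delivered / target = BSA × 178.6 / (357.2 + BSA).

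| BSA (m²) | Portion / batch (g) | Ratio | Delivered vs target (g) | Shortfall |
|---|---|---|---|---|
| 1.5 | 267.90 / 358.7 | 0.747 | 1.12 vs 1.5 | 25% |
| 1.6 | 285.76 / 358.8 | 0.796 | 1.27 vs 1.6 | 20% |
| 1.7 | 303.62 / 358.9 | 0.846 | 1.44 vs 1.7 | 15% |
| 1.8 | 321.48 / 359.0 | 0.895 | 1.61 vs 1.8 | 10% |
| 2.0 | 357.20 / 359.2 | 0.994 | 1.99 vs 2.0 | 0.6% |

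The delivered dose is close to BSA²/2, where 12a intends BSA.

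**Route B: 6.0.2 in bulk, General Formula.** Delivered = 2.0 × (BSA × 178.6) / 359.2 = 0.994 × BSA, a shortfall of 0.6% at every BSA.

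**Concentration in a saved aliquot.**
- Route A: 1000 × BSA / (357.2 + BSA) = 4.18 mg/g at 1.5 m² and 5.01 mg/g at 1.8 m².
- Route B: 1000 × 2.0 / 359.2 = 5.57 mg/g for everyone.

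The frozen aliquots could therefore show which route was used, although no assay of them is stated in this chapter.

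**Above 2 m² the text does not settle the dose.** At 2.2 m² the portion is 392.92 g, and three readings are possible:
- 12a in each of two batches, then mixed: 392.92 / 359.4 = 1.093, or +9%.
- 12a added once, two batches mixed: 392.92 / 716.6 = 0.548, or −45%.
- 12a in the first batch only, that batch drunk whole: 1.00, or no error.

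No error is asserted in that range.

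The day of addition changes none of these amounts.

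**The case against.** The best case against the dosing point is that the numbered order cannot be followed strictly anyway. Step 9 needs a figure that appears only at 12a, so steps 11 to 12a may be meant as sizing notes, worked out beforehand. Step 12 says an amount is calculated; it does not itself tell staff to weigh a portion from the finished batch. The text that puts weighing after step 9 is in 6.0.2. Step 12a is also worded per participant, and the per-batch figure of 2.0 g is printed in 6.0.2. If 12 and 12a are worked together and the 12a amount goes into the weighed portion, the error is zero.

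Part of this stands. The percentages describe what follows from the printed order; they are not evidence that any center worked that way. But the zero-error reading needs an instruction that 6.0.1 does not give. Step 9 acts on the batch, as step 11 confirms by telling staff to repeat steps 2 to 10 for extra formula, and 6.0.2 identifies step 12 as the weighing-out that follows step 9.

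On timing, it can be said that 6.0.2 merely narrows the permission in 6.0.1, which carries a 1990 sign-off, and that a center adding on the test day satisfies both. That is true, but a center using the 24-hour option breaches 6.0.2 while obeying 6.0.1.

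**Conclusion.** Both points hold, and both are minor. The day conflict is direct and appears in current text. The double scaling holds for a one-subject batch prepared in the printed order of 6.0.1, with shortfalls from about 25% at 1.5 m² to 0.6% at 2.0 m². The size depends on the assumed BSA range and on reading 12a in grams. The direction below 2 m² and the near-quadratic form do not depend on the range.

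The practical effect is confined to postprandial retinyl ester levels. Section 1.0.2 does not name them, and Chapter 8 (II.A) says only that some participants may be asked to join the postprandial studies. Each participant eats all three diets with weight held stable, so a constant route gives much the same error in all three tests and largely cancels in the within-person diet contrast. What remains exposed is comparison of retinyl ester levels between persons or centers, and any participant whose preparation route changes between feeding periods. For scale, Chapter 8 (V.D) gives assay coefficients of variation below 7%, which the shortfall exceeds at 1.8 m² and below.

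**What to change.** Reword step 9 of 6.0.1 so that every center adds 2.0 g of Aquasol A to each 357.2 g batch, mixes, and then weighs out the step 12 portion. Equally acceptable is to weigh out the step 12 portion first and then add the 12a amount to that portion; one method should be chosen for all centers and periods. Print the unit in 12a. Delete the 24-hours-before option so that addition is on the test day, which satisfies both sections.

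The cost is one reworded step and one deleted clause. Adding the Aquasol amount and time to form PP2 would be useful but is optional.

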6.0.2 Sampling for Fat Load Test

The fat formula steps 1-8 can be prepared in bulk the day prior to the study. On the day of the study, after Step 9, the amount of formula needed for each subject could be weighed out -- Step 12. Three 5 to 10g aliquots must be saved -- Step 13.

General Formula:

Cream-Whipping-Heavy	190 gms
Ice Cream - 10% Fat	90 gms
Syrup Choc Flavored	30 gms
Promod	25 gms
Safflower Oil	22 gms
5 drops Lactaid	0.2 gms
Aquasol (vitamin A)	2.0 gms

Formula must be made 24 hours prior to serving so that all lactose can be converted to glucose and galactose by Lactaid.

[figure not shown]
1. Heavy cream: Tuscan Ultrapasteurized Heavy Cream Grade A
 1 Tbsp (15 ml) = 50 calories
 6g fat
 3g SFA
 10mg cholesterol
 5mg Na⁺
 10% fat ice cream is Breyer's Vanilla
 Syrup is Nestle's Quik - you can also use the Strawberry flavor
2. Vitamin A (Aquasol) must be added on the day of the study. Aquasol A drops .1ml has 5000 usb is manufactured by Armaur Pharmaceutical Co. Kankakee, Illinois 60901 for ASTRA USA Inc., Westborough, MA 01581.

Promod is from Ross Laboratories, Columbus, OH.

Figure 6.0.2.1 Nutrient Values

Nutrient Values			
+ Kilocalories	1237 kc	Protein	32.714 Gm
+ Carbohydrate	47.786 Gm	+Fat	105 Gm
Fiber-Crude	0.060 Gm	+Cholesterol	300 Mg
+Saturated Fat	52.008 Gm	Oleic Fat Acid	22.811 Gm
+Linoleic FA	18.154 Gm	+Sodium	240 Mg
+Potassium	725 Mg	Magnesium	42.252 Mg
Iron	0.611 Mg	Zinc	1.630 Mg
Vitamin A	3161 IU	Vitamin D	190 IU #
Vitam. E/Total	9.899 Mg	Vitamin C	1.575 Mg
Thiamin	0.085 Mg	Riboflavin	0.455 Mg
Niacin	0.323 Mg	Vitamin B6	0.093 Mg
Folate	10.415 Ug	Vitamin B12	0.765 Ug
+Pantoth. Acid	0.931 Mg	Calcium	247 Mg
Phosphorus	402 Mg	+Tryptophan	181 Mg
+Threonine	512 Mg	+Isoleucine	623 Mg
+Leucine	994 Mg	+Lysine	814 Mg
+Methionine	227 Mg	+Cystine	130 Mg
+Phenylalanine	583 Mg	+Tyrosine	536 Mg
+Valine	764 Mg	+Histidine	281 Mg
Alcohol	0.000 Gm	Ash	1,964 Gm
+Copper	0.289 Mg #	+Manganese	0.114 Mg #
Iodine	35.120 Ug #	+Mono Fat	25.454 Gm
+Poly Fat	19.184 Gm	Caffeine	4.200 Mg
+Fluoride	57.000 Ug #	+Molybdenum	No Data #
Vitamin K	11.336 #	Selenium	0.001 Mg #
+Biotin	0.057 Ug #	+Chloride	No Data #
+Chromium	No Data #	Sugar	27.485 Gm
Fiber-Dietary	0.071 Gm	Vit. E/AT	7.542 Mg #

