- a. Circle YES or NO. If NO, go to question 32.
- b.-d. If YES, list the specific foods mentioned.

Question 32: Special Diets

- a. Circle YES or NO. If NO, go to question 33.
- b.-f. If YES, read through the list provided and circle YES or NO, or UNSURE. If YES or UNSURE is circled for any special diet, review by medical personnel is required.
- g. Responses coded F should be described in more detail.

Question 33: Alcohol Consumption

- a. Circle YES or NO. If NO, go to question 34.
- b. If YES, enter the number of drinks the applicant consumes in a seven day week (weekdays and weekends together). Note: 1 drink = 1, 5 oz. glass of wine; 1, 12 oz. serving of beer; or a 1.5 oz. shot of liquor. Enter 0 for less than 1 drink per week. If the answer is greater than 12, the applicant has become ineligible. Thank the applicant for his/her interest, terminate the interview, and complete questions 12 - 13.

Questions 34-36: Body Mass Index (BMI)

34. Enter the applicant's height in feet and inches. Height should be without shoes rounded to the nearest inch.
35.
 - a. Enter applicant's weight in pounds. Weight should be without shoes, rounded to the nearest pound.
 - b. Find the applicant's height in the BMI table provided in the DELTA Forms Guide. Circle YES or NO.

If the applicant's weight is greater than the upper limit listed for his/her height the applicant is ineligible for the study. Thank the applicant for his/her time and interest, terminate the interview, and complete questions 12-13.

36. Circle YES or NO. If the applicant indicates NO, emphasize again that this study requires participants **not** to lose or gain weight. If the applicant affirms NO to this question he/she has become ineligible for the study. Thank the applicant for his/her time and interest, terminate the interview, and complete questions 12-13.

Questions 37-39: Women born after 1943 only

Circle YES or NO. If YES to any of these questions, the applicant is no longer eligible for the study. Thank the applicant for her time and interest, terminate the interview, and complete questions 12-13.

At this point in the interview, if the applicant remains eligible for the study, read him/her the general description of the DELTA study located in the DELTA Forms Guide.

Question 40: Further Interest

- a. Circle YES or NO.

If YES go to questions 41 & 42. Schedule the applicant for Eligibility Visit 1 and enter this information under question 12 of this form.

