b. Is the applicant's weight recorded in question #35a greater than the
upper weight limit for the applicant's height in the height/weight tables? YES NO

36. It is important that our participants not lose or gain weight in this study. Are you
willing to participate in a study where your weight is maintained at the same level it is
now?
YES NO

[If the answer to question 35b is yes, or the applicant is not willing to maintain the same
weight during the study, then the applicant has become ineligible. If so, terminate the
interview and complete questions 12-13].

Telephone Screening Form

Form Code: TSV
Version B 5/10/94

WOMEN BORN AFTER 1943 ONLY

37. Are you pregnant or planning to become pregnant within the next year?
YES NO

38. Are you breastfeeding? YES NO

39. Have you had a baby within the last 6 months? YES NO

If the answer to either question 37, or 38, or 39 is YES, then the applicant has become ineligible. If so, terminate the interview and complete questions 12 and 13.

Telephone Screening Form

Form Code: TSV
Version B 5/10/94

[Interviewer: If applicant is still eligible at this point, read the general description of the DELTA Study in the Forms Guide and continue the interview.]

FURTHER INTEREST

40a. Based on your understanding of the study at this point, would you be interested in coming to the center to learn more about this study and to have some blood work done and your blood pressure checked to determine if you remain eligible?

YES (go to question 41) NO

[If NO] What is the reason? [Circle YES or NO for reasons for not scheduling Eligibility Visit 1]:

- | | | |
|---|-----|----|
| b. Uninterested in general study protocol | YES | NO |
| c. Unwilling to commit due to length of study | YES | NO |
| d. Unwilling to come to feeding center for 2 meals each day for 5 days each week | YES | NO |
| e. Unwilling to eat study food | YES | NO |
| f. Unwilling to limit intake to study foods only | YES | NO |
| g. Unwilling to allow maintenance of current body weight | YES | NO |
| h. Lives too far from feeding center | YES | NO |
| i. Travels out of town as part of job position or has travel plans for study period | YES | NO |
| j. Unwilling to submit to frequency of blood draws | YES | NO |
| k. Other (I. specify: _____) | YES | NO |

[Interviewer: If applicant is not interested, terminate interview and complete questions 12-13.]

Telephone Screening Form

Form Code: TSV
Version B 5/10/94

SCHEDULING ELIGIBILITY VISIT 1

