m. lung disease, chronic bronchitis, emphysema	Y	N	U
n. acquired immune deficiency syndrome (AIDS) or positive HIV test	Y	N	U
o. cancer (active within 5 years)	Y	N	U

Please be sure to answer 23 a, and b, and c!

23 a. Do you have thyroid disease or a thyroid problem? Y N U

b. Have you ever had treatment, such as radioactive iodine or surgery for a thyroid problem? Y N U

c. Are you taking any medication for your thyroid? [If unsure, check medications.] Y N U

[If any medical condition was circled YES or UNSURE, then review by medical personnel is required to exclude applicant from participation.]

Medical reviewer Initials: _____ Eligible: YES NO Date ____ / ____ / ____

Eligibility Visit 1

Form Code: EV:
Version B 5/10/94

24. a. Are there any medical reasons that might interfere with your ability to participate?
(Examples: hospitalized on a regular basis, scheduled surgery, family medical problems)
YES NO [If NO go to question 25.]

b. If YES, describe: _____

25. a. Are there any personal reasons that would keep you from participating?
(Examples: family problems, vacation scheduled during study period, child care difficulties, religious reasons) YES NO [If NO go to question 26.]

b. If YES, describe: _____

26. a. Are there any professional reasons that would keep you from participating?
(Examples: job related travel out of town, work irregular shifts or night shift)
YES NO [If NO go to question 27.]

b. If YES, describe: _____

If the answer to questions 24, or 25, or 26 is YES, inform Study Coordinator.

Eligibility Visit 1

Form Code: EV1
Version B 5/10/94

WOMEN ONLY

27. a. Are you currently taking an oral contraceptive? YES NO
- b. If YES to 27a, are you planning to stop? YES NO
- c. If NO to 27a, are you planning to start? YES NO

[Circle the letter preceding the response.]

28. What is your current menstrual status?

- R Regular (normal) [go to question 30]
I Irregular [go to question 29a]
N Not menstruating [go to question 29c]

29. a. If you are menstruating irregularly, what is the reason?

- A Undergoing menopause
B Other

b. If Other, describe _____

c. If you are not menstruating, what is the reason?

- A Natural menopause
B Hysterectomy
C Medication stopped period
D Other (d. describe _____)

30. When did you have your last period?

- A Less than 2 months ago
B 2 months to 6 months ago
C 6 months to 1 year ago
D 1 year but less than 3 years ago
E At least 3 years ago

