3.7 ELIGIBILITY VISIT 2 (EV2)

3.7.1 Purpose

1. To answer additional questions the applicant may have about the study.
2. To determine continued eligibility.
3. To measure blood pressure.
4. To measure weight and height circumferences.
5. To determine appliance availability.
6. To perform the fasting blood draw for Lipid profile, Insulin, Glucose, TSH, Chemscreen.
7. To schedule callback to applicant to communicate eligibility for the Diet Run-In Visits, Randomization and Feeding Period following determination of eligibility.

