3.8 MENSTRUAL CALENDAR

This information will be kept in the participant's file to ensure that accurate dates of the menstrual cycle are recorded on the Participant Weekly Monitoring Form (PWM).

The calendars should be kept current during the 7 weeks of the diet trial. If you distribute them to the subjects, you should plan to collect them at the final (week 7) blood draw for each subject. Alternatively, you may choose to keep the calendar in the subject file and update it at each visit.

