In 12a, circle either YES or NO. A change in smoking habits is defined as started smoking, stopped smoking, or increased or decreased smoking by at least 50 percent. If the response to 12a is NO, go to question 13. If the response to 12a is YES, then proceed with 12b and circle one letter only corresponding to the correct response. *(Note to interviewer: If 12a is answered YES, inform the Study Coordinator.)*

Question 13: Women Only *(Answered based on information from the week preceding the first weekly interview.)*

In 13a, circle either YES or NO. If the response to 13a is YES, then proceed with 13b and 13c, recording the date and circling the day of the week the participant began menstruating. *(Note to interviewer: This question should be skipped completely for men participants as well as for clearly postmenopausal women participants. NA is not needed as a response.)*

Reminder to All Study Personnel: Be sure to complete this form for each participant at the time of the last blood draw of the feeding period.

Participant Weekly Monitoring

Form Code: PWM
Version B 5/10/94

DELTA ID: _____

Monday's DATE: ____/____/____
[THIS WEEK] (mm/dd/yy)

1. Code Number of personnel completing this form: _____

BLOOD DRAW

[Complete numbers 2-4 during weeks 5, 6, 7.]

2. Period 1 2 3 [Circle correct number]

3. Week 5 6 7 [Circle correct number]

4. Date of blood draw ____/____/____
mm/dd/yy

WEIGHT [THIS week]

[Participants are weighed before dinner, without shoes or coats.]

5. a. Date of first weekly weight: _____
(mm/dd/yy)

First weekly weight, either in lbs or kg:

b. lbs: _____ or c. kg: _____

d. Current calorie level: 1500 2000 2500 3000 3500 [Circle correct number]

6. a. Date of second weekly weight: _____
(mm/dd/yy)

Second weekly weight, either in lbs or kg:

b. lbs: _____ or c. kg: _____

d. Current calorie level: 1500 2000 2500 3000 3500 [Circle correct number]

Be sure to administer this form at the last blood draw of the period!

Figure 4.5.2: Participant Weekly Monitoring

Participant Weekly Monitoring

Form Code: PWM
Version B 5/10/94

[Interviewer: Ask the participant the rest of the questions based on their activities during the past week.]

EXERCISE [Exercise is recorded at the first weekly visit following the weekend.]

7. a. In the past week, has your exercise level changed? YES NO [If NO go to question 8]
b. If YES, how has your exercise level changed: [Circle letter preceding your selection]

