A...More active B...Less active C...No exercise

If the answer to question 7a is YES, inform the Study Coordinator.

MEDICATION

8. a. Have you taken any medications in the last week? YES NO [If NO, go to question 9]

If YES, specify the name of the medication and amount of medication:

b. Medication: _____ c. Total weekly amount: _____

Reason _____

d. Medication: _____ e. Total weekly amount: _____

Reason _____

f. Medication: _____ g. Total weekly amount: _____

Reason _____

9. a. Have you taken any vitamin, mineral or other nutritional supplements in the past week?
YES NO [If NO go to question 10]

If YES, specify name and amount:

b. Name: _____ c. Total weekly amount: _____

d. Name: _____ e. Total weekly amount: _____

If the answer to either question 8 or 9 is YES, inform the Study Coordinator.

ILLNESS

10. Have you been ill in the last week? YES NO [If NO go to question 12]

If YES, describe illness: _____

11. a. In the past week did your eating change as a result of any illness?
 YES [If Yes, enter reasons in space provided.] NO [If NO go to question 12]

b. If YES to 11a, was a diet history taken? YES NO

c. If YES to 11a, was any action taken? YES NO

If the answer to question 11 is YES, inform the Study Coordinator.

SMOKING HABITS

12. a. In the last week, have your smoking habits changed? YES NO [If NO go to question 13]

[A change in smoking habits is defined as started smoking, stopped smoking, or increased or decreased smoking by at least 50 percent.]

b. If YES, how have your smoking habits changed? [Circle letter preceding the selection.]

- A...Smoking more
- B...Smoking less
- C...Quit smoking
- D...Started smoking

If participant reports any changes in smoking habits, inform Study Coordinator.

Participant Weekly Monitoring

Form Code: PWM
Version B 5/10/94

WOMEN ONLY

13. a. Did you begin menstruating during the last week? YES NO

b. If YES to 13a, what date did you begin menstruating: _____
(mm/dd/yy)

c. If YES to 13a, what day of the week did you begin menstruating?
(Circle the number preceding the answer)

1. Monday 2. Tuesday 3. Wednesday 4. Thursday

5. Friday 6. Saturday 7. Sunday

Be sure to administer this form at the last blood draw of the period!

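### Pregnancy is an exclusion, but the forms shown ask about it directly only by telephone, weeks to months before three vitamin A fat loads, and no printed action follows a missed period

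*Protocol*

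**What the plan says.** Telephone screening Q37, put to women born after 1943, reads "Are you pregnant or planning to become pregnant within the next year". The instructions for Questions 37-39 make the answer decisive: "If YES to any of these questions, the applicant is no longer eligible for the study".

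Later contacts touch the subject only indirectly:
- **Eligibility Visit 1:** Q27 covers oral contraceptives, Q28-29 cover menstrual status and the reason for irregular or absent menses, and Q30 asks "When did you have your last period". Pregnancy is not in the list of medical conditions.
- **Eligibility Visit 2:** section 3.7.1 gives the blood work as "To perform the fasting blood draw for Lipid profile, Insulin, Glucose, TSH, Chemscreen". No pregnancy test is listed.
- **During feeding:** item 13 of the Participant Weekly Monitoring form (PWM) asks "Did you begin menstruating during the last week". Section 3.8 adds a calendar, either updated by staff at each visit or handed out; if handed out, "you should plan to collect them at the final (week 7) blood draw for each subject". Section 5.4.6 uses menstrual timing only to interpret weight gain.

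The PWM notes send changes in exercise (item 7), medication or supplements (8-9), illness-related eating (11) and smoking (12) to the coordinator. For smoking the wording is "If 12a is answered YES, inform the Study Coordinator". Item 13 has no such note.

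Section 6.0.1, step 12a, scales Aquasol A by body surface area, and section 6.0.2 gives its strength as "Aquasol A drops .1ml has 5000 usb". Forms PP2 and PPF place the fat load in week 7, while Chapter 8, Table 4 says week 6 or 7. PP2 runs from the fasting sample (item 4) to the weight of drink offered (item 5).

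**The concern.** The protocol makes pregnancy disqualifying but, in what is shown, tests that rule once, before enrolment, in a study that runs for months afterwards. Q37's one-year horizon captures intention; it cannot capture an unplanned conception. The fat load is the one study procedure that adds a concentrated vitamin A preparation, and it is repeated in each of three periods. Premenopausal women are not kept out of it.

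The information that would raise the question is already collected, but nothing is attached to it. A participant who reports a vitamin tablet is referred to the Study Coordinator; one whose weekly forms show no period is not. Followed as printed, the forms would let the drink be given to a woman whom the protocol itself treats as ineligible, possibly with a record of a missed period already in staff hands.

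**Working it through.** **The plan's own figure.** Step 12a gives Aquasol = body surface area x 2 / 2. At the reference 2 m2 this is 2 x 2 / 2 = 2.0 g, which matches the general formula in 6.0.2. The rule is therefore 1 g per m2.

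**Dose.** 5,000 units per 0.1 ml = 50,000 per ml. Dose = (grams / density) x 50,000. The protocol gives neither a density nor a body-surface range, so these are assumed:
- 1.6 m2 at 1.0 g/ml: 1.6 x 50,000 = 80,000
- 2.0 m2 at 1.0 g/ml: 2.0 x 50,000 = 100,000
- low end, 1.6 m2 at 1.1 g/ml: 1.6 / 1.1 x 50,000 = 72,727
- high end, 2.0 m2 at 0.9 g/ml: 2.0 / 0.9 x 50,000 = 111,111

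The nutrient table (Figure 6.0.2.1) lists 3,161 IU of vitamin A. That is less than 0.1 ml of Aquasol supplies, so the table cannot include the added 2 g and does not contradict this range.

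**Time from the telephone question to the drink.** Section 3.0 puts telephone screening at any time, EV1 at least one week after the applicant's initial contact, and EV2 one to four weeks after EV1. The telephone screen could fall just before EV1, so the firm floor counts only the one week from EV1 to EV2. Feeding starts on 30 September 1994, 6 January 1995 (+14 weeks) and 31 March 1995 (+26 weeks). Week 6 begins 5 weeks into a period and week 7 begins 6 weeks in.

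| Period | Start of week 6 | Start of week 7 |
|---|---|---|
| 1 | 1 + 0 + 5 = 6 weeks | 1 + 0 + 6 = 7 weeks |
| 2 | 1 + 14 + 5 = 20 weeks | 1 + 14 + 6 = 21 weeks |
| 3 | 1 + 26 + 5 = 32 weeks | 1 + 26 + 6 = 33 weeks |

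The three-day run-in adds about 0.4 week. If the telephone screen was the initial contact, add one week: 7-8, 21-22 and 33-34.

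**Would the menstrual record help?** By the start of week 6 or 7 a period's calendar has run 5 x 7 = 35 or 6 x 7 = 42 days. At the typical 28-day cycle printed on the calendar, at least one period has fallen due, so a look at the record is informative. It would not show a conception in about the last two weeks (assumed).

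**How many loads.** Table 1 plans 23 premenopausal women, so the ceiling is 23 x 3 = 69 loads. Chapter 8, II.A says only some participants may be asked to take part, so the actual number may be lower. These are loads given to premenopausal women, not exposed pregnancies, for which the protocol offers no basis for an estimate.

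**The case against.** The strongest reply is that the fat load stands out only because of its vitamin A, and nothing in the protocol calls that dose hazardous. This stands as a limit. A reader might infer that the protocol gives a dose known to be harmful in pregnancy; the documents do not say so. The point does not need it, because the unenforced exclusion is the protocol's own.

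A reader might also infer that nobody checks before the drink. The documents do not support that either:
- Consent forms, Participant Agreements and the Forms Guide are not shown and may carry a warning or a duty to report.
- PWM must be completed at the last draw of the period, and handed-out calendars are submitted there. That is week 7, the week printed on PP2 and PPF, and Table 4 places the load on a fasting-draw day. For a week 7 load, both records are due at that week's draw.
- EV1 Q27 covers contraceptive use. Section 1.1.5 has investigators monitor safety continuously and gives each center a Medical Officer.
- The phlebotomy form checks fasting and alcohol, and a reminder with PP2 asks for body surface area to be rechecked after weight change.

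All this is fair, but none of it ties an action to a missed period or asks about pregnancy before the load. Nothing printed requires the records to be read before the drink.

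Finally, repeating Q37 word for word would withhold loads from women merely planning pregnancy after the study. An automatic hold for every missed period would catch women whose irregular or medication-stopped cycles EV1 already recognises. Both objections are accepted in the fix.

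**Conclusion.** The point holds, limited to the procedures and forms shown. Pregnancy is disqualifying but is asked directly only by telephone, at least about 6-7, 20-21 and 32-33 weeks plus run-in before the three loads. Each load carries about 73,000-111,000 units, given the assumed body surface area and density and the reading of the printed unit as USP. Menses are recorded, but no printed action follows a missed period, and PP2 has no pregnancy item before the drink.

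This is a safety-procedure gap that should be closed. It is not evidence that anyone was or would be harmed; the clinical significance of the dose belongs to the Medical Officers. It does not affect the fasting endpoints or the design.

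**What to change.** 1. **PP2, before item 5,** for women not clearly postmenopausal, ask: *Are you, or could you be, pregnant now?* (YES / NO / UNSURE), without the one-year planning horizon. Staff also review PWM item 13 and the calendar before the drink.
2. **Hold rule.** Hold the load until the Medical Officer clears it if the answer is YES or UNSURE, or if a period was missed and is not explained by a cycle pattern or medication already recorded at EV1 Q28-29.
3. **PWM item 13.** Add: *If an expected period was missed, inform the Study Coordinator.*
4. **Week 6 loads.** If a load is given in week 6, have any handed-out calendar brought to that visit.

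No change in dose is proposed. A pregnancy test on the first-morning urine already collected in weeks 6 and 7 is optional, depends on consent, and is not part of the required change.

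The cost is one PP2 item, one PWM line and an occasional lost fat-load result. That result is a secondary endpoint, and its loss leaves that woman's three-diet fat-load comparison incomplete. The fasting sample is drawn before the drink and is unaffected. No visit or blood draw is added.
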